4.3.4 Participant Recruitment and Stratification

For the pilot testing, recruitment of patients will be stratified into the following 3 groups:

Aggressive lymphomas: 20 patients

Acute leukemias: 20 patients

Myeloma, Chronic lymphocytic leukemia (requiring treatment), chronic myeloid leukemia: 10 patients

We will target a population that exceeds the following diversity thresholds: 30% non-white race, 50% female, 25% rural.

For the qualitative interviews, recruitment of patients will be stratified into the following 2 groups:

1. Those participants who believe that “Living longer” is the most important attribute (n=10),

and

2. Those participants who believe another attribute is the most important attribute (n=10).

Recruitment of clinicians will be as follows:

Oncology clinicians (including physicians, advanced practice providers, nurse navigators): 2-5

Palliative Care clinicians (including physicians, advanced practice providers, nurse navigators): 2-5

4.3.5 The BWS survey

Priorities are how people value and rate the importance of multiple goals. In comparison, patient preferences reflect choices that patients make among several alternatives based on the expected benefit they get from each alternative. BWS surveys, a type of conjoint analysis, are one of several methods to measure

preferences. They are emerging as potentially important tools to elicit preferences of patients in the clinical setting.²⁰ BWS surveys involve asking participants a series of questions where they choose one attribute that is best and one attribute that is worst. In this survey, we will be asking patients to choose between the following 7 attributes:

- a. Maintaining usual activities
- b. Living longer
- c. Avoiding becoming dependent upon others
- d. Avoiding short-term side effects
- e. Avoiding long-term side effects
- f. Avoiding hospitalizations
- g. Avoiding high out-of-pocket costs

We will be using a BWS survey that is adapted from a BWS survey we used to capture the preferences of patients with AML. Sampling 832 patients with the BWS survey, we illustrated that patients had the strongest concerns about treatment outcomes in psychosocial and physical domains.³² Patients were most worried about dying from their disease, the long-term side effects of treatment, and becoming a burden to others.

4.3.6 Longitudinal Assessments

Participants will complete longitudinal assessments every 2 weeks (x 5). These assessments will include the BWS survey, CollaboRATE, WIWI, Decisional conflict scale, EQ-5D-5L, distress thermometer, and 7 items from the PRO-CTCAE. These assessments will begin after a treatment discussion with their oncology clinician.

The first longitudinal assessment will include a follow-up questionnaire that will assess patient acceptability and preliminary efficacy of the BWS to improve treatment decisions.

Participants will be given a \$10 electronic gift card for each assessment.

4.3.7 Extended Assessments

After completing the longitudinal assessments (x6), participants will complete extended assessments every 3 months for the next 2 years (up to 7 assessments). These extended assessments will include the same questionnaires as the longitudinal assessments.

At 1 year on the study (the third extended assessment), participants will complete the 1 year questionnaire.

Participants will be given a \$10 electronic gift card for each assessment.

4.3.8 Qualitative Interviews

Patients:

The qualitative interview will establish content validity of the BWS by cognitive interviews that will explore patients understanding of the content of the BWS.

Specific domains to be covered will include:

- Cognitive interview to evaluate patient understanding of each of the questions asked within the BWS
- subjective value of potential outcomes including attributes elicited in BWS
- patient understanding of how preferences influenced treatment decisions including elicitation of important factors in the decision (if applicable),
- expected outcomes,
- additional attributes not included in the BWS, and
- preferences for potential interventions to improve preference elicitation and decision-making.

In addition to open ended questions as part of the interview, patients will complete a digit span test to test working memory and recall.

The follow-up qualitative interview will cover the same content as the first interview in addition to asking participants to reflect upon how their experience has changed over the time period between interviews.

Interviews with clinicians will explore barriers and facilitators of implementation of surveys to capture patient values and preferences. There is no follow-up interview with clinicians. Clinicians will not complete the Digit span test.

Interviews will be recorded to allow for qualitative analysis. Transcripts of the interviews will be made. The interviews should take about 30 minutes to complete. Following the interview a codebook will be created with emerging themes to allow for qualitative analysis similar to previous studies.¹¹

4.3.9 Participant questionnaires

4.3.9.1 Baseline Participant Questionnaire

Participants will complete a baseline questionnaire online via PRO Core upon enrollment. Questions related to the following domains will be asked of patients: race; ethnicity; household income; and insurance. This baseline questionnaire will

also include the PROMIS Cognitive Function 8a short form (8 items) to assess the perceived cognitive impairment of patients.

4.3.9.2 Decisional conflict scale (DCS):

Decisional conflict will be evaluated with the validated survey measure decisional conflict scale.^{31,33} Patients will complete the subscales of decision uncertainty (3 items) and perceived effective decision making (4 items).

4.3.9.3 EQ-5D-5L:

Health-related quality of life will be evaluated with the validated survey measure EQ-5D-5L.³⁴ This is a 5 question survey.

4.3.9.4 PRO-CTCAE:

Symptoms will be evaluated with the validated survey measure PRO-CTCAE.³⁵ Patients will complete the following 7 items: pain, fatigue, nausea, vomiting, constipation, diarrhea, appetite.

4.3.9.5 PROMIS emotional distress short-form 8a

The PROMIS emotional distress short-form 8a is a 8 question survey developed to understand current emotional distress among patients and validated in numerous settings.

4.3.9.6 Follow-up Questionnaire

Patient acceptability and preliminary efficacy (both defined above) will be assessed in this 2-item study-specific questionnaire.

4.3.9.7 1 year Questionnaire

Patient acceptability and preliminary efficacy (both defined above) will be assessed in this study-specific questionnaire. Additionally, patients will be given open ended questions reflecting on how the BWS survey influenced the treatment decisions with their providers.

4.3.9.8 CollaboRATE:

Preference clarity will be evaluated with the validated survey measure CollaboRATE.³⁰ This is a 3 question survey.

4.3.9.9 WIWI

The “was it worth it” (WIWI) patient questionnaire is a subjective tool to assess a patient’s decisional regret related specifically to the chemotherapy decision.³⁸ We

will use two questions to avoid overlap with other questionnaires: Was it worthwhile for you to undergo chemotherapy? And If you had to do it over, would you undergo chemotherapy again?

4.3.9.10 Decision Regret Scale (DRS):

Decisional regret will be evaluated with the validated survey measure DRS.²⁹ This is a 5-item questionnaire that has been validated as an important outcome measure of preference/value clarification measures.

4.3.9.11 Digit Span Test:

The forward and backward assessments of the Digit Span test are subsets of the Wechsler Intelligence Scale, and when used separately, are considered validated measures of working memory.^{39,40} Participants are assessed on their ability to repeat strings of numbers, increasing in length by one, until an error occurs on the reiteration of the string, or they reach a string length equal to 9. Participants will run through all forward strings before moving to the digit span backwards test, in which they will be asked to repeat strings of numbers in reverse order.

4.3.9.12 Provider questionnaire

This survey will include 3 questions to capture treatment intent (curative vs. palliative), provider's assessment of which outcomes are most important to the patient, and outcomes most important to treatment decision making.

4.4 Expected Risks

4.4.1 Physical Risks

No physical risks are expected with this study.

4.4.2 Emotional Risks

Some questions in the patient questionnaires or interviews could create emotional distress or confusion. Patients will be instructed that the questionnaires are for research purposes only and any problem or symptom should also be reported to their physician or nurse.

4.4.3 Patient Confidentiality

We do not anticipate any breach of confidentiality. Any information about the participants obtained from this research will be kept as confidential as possible. All data obtained will be stored on a secure server.

4.5 Removal of Participants from Protocol

Participants will be removed from the protocol if they decide they no longer want to participate in the study.

5.0 TIME AND EVENTS TABLE

5.1 Time and Events Table

	Study Enrollment	Interim	Longitudinal/ Extended assessments	Qualitative Interviews
Screening	X			
Informed Consent	X			
HIPAA	X			
Enrollment Questions	X			
Decision Self-Efficacy	X			
Values subscale of DCS	X	X (if not completed at enrollment)	X	
BWS	X	X (if not completed at enrollment)	X	X
Baseline Questionnaire	X	X (if not completed at enrollment)		
PROMIS cognitive function	X	X (if not completed at enrollment)		
EQ-5D-5L	X	X (if not completed at enrollment)	X	
PRO-CTCAE	X	X (if not completed at enrollment)	X	
PROMIS emotional distress	X	X (if not completed at enrollment)	X	
Follow-up Questionnaire			X (First timepoint only)	
CollaboRATE			X	
WIWI			X	
DRS			X	
1 year Questionnaire			X (3 rd extended assessment)	
Qualitative interview				X
Digit Span Test				X (Patients only)

Provider assessment	
	Study Enrollment
Screening	X
Informed Consent	X
HIPAA	X
Provider Questionnaire	X

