4.3 Study Details

4.3.1 The study will recruit 50 total participants and conduct qualitative interviews on a subset of 20 participants.

4.3.2 **Pilot testing:** The study team will review the inpatient census and clinic schedule to evaluate for potentially eligible patients. The study team will confirm patient eligibility with the primary oncologist or principal investigator. Eligible patients will be sequentially approached to be recruited to this study until 50 patients are recruited who complete BWS survey.

Upon enrollment, the study team will record information about patients obtained from the patient or the medical record including gender, age, lab values including complete metabolic profile, complete and differentiated blood counts, albumin, LDH, a1c, cholesterol levels, hematopathology reports, clinician-determined performance status (Karnofsky and ECOG), and comorbidities present.

Demographic information such as age, sex, and zip code will be obtained.

Once consented, patients will complete initial study questionnaires within PRO Core either remotely if able or in-person with the assistance of study staff prior to a clinic visit. For patients who decline to participate in the study, reasons for refusal will be anonymously collected to examine the issue of selection bias as well as to assist with determination of feasibility.

After the clinic visit, patients will be prompted to complete the first longitudinal assessment via PRO Core. This will be available for 7 days. The treating oncologist who saw the patient will be prompted to fill out an assessment via email. Clinicians may receive multiple reminder emails to complete the survey to improve completion rates. We will collect provider responses within 2 weeks of initial patient survey.

Following, every 2 weeks (up to 5 times) participants will be prompted in PRO Core to complete the longitudinal assessment survey. Then, the extended assessment survey will be delivered by PRO Core every 3 months for up to 2 years (7 times).

Retention:

Multiple strategies will be utilized to retain patients on study.

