1. *Provide Detailed Rationale of the Study and Study Brochure:* Upon enrollment participants will be informed of the rationale of the study: to help understand what is most important to each patient to tailor therapy to patient preferences. Patients will be informed that their responses will help adapt the survey that they will receive to help future patients. They will be given printed information about the study if recruitment is done in person.

2. *Training:* Each patient will receive training on how to complete the assessments in PRO Core. This will take place during enrollment (either in person or remotely).
3. *Reminders to complete the initial post-visit assessments:* The day after the treatment encounter, patients will receive an automated reminder to complete the assessments.
4. *Reminders to complete the follow-up assessments:* Staff will direct them to complete the assessment remotely via a secure link sent by email. PRO Core will send patients a reminder daily for up to 2 days in case of non-response. Study staff will call patients if no response.
5. *Reminders in case of non-response:* Study staff will call patients if no response.
6. *Support to complete assessments:* Staff will assist participants to log-on to PRO Core and to complete assessments if needed.
7. *Compensation:* Participants will be provided with a \$10 gift card following completion of each longitudinal and extended assessment.

4.3.3 **Qualitative Interviews:** Based on responses to the survey, 20 patients will be selected to complete interviews. Patients will complete an initial interview and a follow-up interview.

The study team will review patients who have consented to the study and confirm eligibility with the primary oncologist or principal investigator. Study staff will call eligible patients to participate in the interviews until the number of desired participants has been reached (n=20) according to the inclusion criteria above and recruitment goals below.

We will use purposive sampling to stratify participants based on the results of the BWS survey. We will stratify into two groups of 10 participants each:

1. Those participants who believe that “Living longer” is the most important attribute,

and

2. Those participants who believe another attribute is the most important attribute.

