7.3.2 Secondary Aims

Patient acceptability:

We will conclude the BWS is acceptable if $\geq 70\%$ of patients (35/50) report that it is acceptable. Hypothesizing 80%, the exact binomial 95% CI will be 66.3-90.0%.

Preliminary efficacy:

We will conclude the tool is potentially efficacious if efficacy (defined as participants answering “moderately effective/very effective” to the question: “How effective was the survey to help you and your doctor choose a treatment that was consistent with your goals?”) is reached in $>50\%$ of patients. Estimating 5-7% missing data from enrollment to initial longitudinal questionnaire (from other PRO assessments in advanced cancer patients^{45,46}) and hypothesizing a rate of 75%, the exact binomial 95% CI will be 60.0-86.6%.

Preliminary completion rates:

Frequencies will be reported at each time point. Completion rate out of the original 50 participants will be reported at each month with exact binomial 95% CIs with reasonable precision, no wider than $\pm 14.5\%$. Reasons for dropout will be summarized as available. Associations of baseline patient characteristics with completion rates will be explored using Wilcoxon Rank sum and Kruskal-Wallis tests.

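### The two items behind the acceptability and preliminary-efficacy rules are asked near the decision only once, at LA1 in a 7-day window, with no catch-up for patients still followed

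*Combined protocol and SAP*

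**What the plan says.** Section 4.3.6 places the two items: "The first longitudinal assessment will include a follow-up questionnaire that will assess patient acceptability and preliminary efficacy". Section 4.3.9.6 says that both outcomes "will be assessed in this 2-item study-specific questionnaire". In Table 5.1 the row for this form has one entry, "X (First timepoint only", and nothing in the Interim column. Section 4.3.2 says of the first longitudinal assessment: "This will be available for 7 days". No text extends that window or carries the items to LA2.

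Seven enrollment instruments in the same table have a second chance in the Interim column: "X (if not completed at enrollment".

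The retention list in section 4.3.2 supports completion: "The day after the treatment encounter, patients will receive an automated reminder to complete the assessments"; "Study staff will call patients if no response"; and staff will help patients log on and complete the forms.

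The 1 year Questionnaire (sections 4.3.7 and 4.3.9.7) assesses both outcomes again at the third extended assessment. Section 4.5 removes patients only at their own wish, so a missed form does not end follow-up.

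Section 7.3.2 states the acceptability rule: "We will conclude the BWS is acceptable if $\geq 70\%$ of patients (35/50) report that it is acceptable". The efficacy rule is more than 50% of patients, with no denominator given. The same section expects 5-7% missing data by the initial longitudinal questionnaire, but mentions this only under efficacy.

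**The concern.** A patient who misses LA1 is prompted again about two weeks later with a battery that lacks these two items. The next request for them comes at about one year, from those still participating, about a decision long past. The study therefore gives up near-decision answers from people it is still contacting every two weeks, although it already uses a catch-up rule for other forms.

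The consequence depends on something section 7.3.2 leaves open. If missing forms stay in the denominator of 50, each one counts as a patient who did not find the survey acceptable. If they leave the denominator, the rule is judged on those able to answer in the week after the treatment decision. Recruitment draws on the inpatient census (section 4.3.2), and 20 of the 50 places are for acute leukemia (section 4.3.4). It is a reasonable inference, not a documented rate, that some of the sicker patients would be among the non-responders.

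**Working it through.** **Inputs from the plan (section 7.3.2).** Acceptability: hypothesized 80%, rule 35/50, exact 95% CI 66.3-90.0%. Efficacy: hypothesized 75%, rule above 50%, exact 95% CI 60.0-86.6%. Missing by the initial longitudinal questionnaire: 5-7%, that is 50 × 0.05 = 2.5 to 50 × 0.07 = 3.5 patients, or about 3-4.

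**Step 1: reproduce the plan's intervals (Clopper-Pearson).**
- Acceptability, 40/50: 66.28-89.97%. This matches, with no missing forms.
- Efficacy, 75% of n = 46 (non-integer count 34.5): 60.05-86.58%. This matches. 46 is 50 × 0.93 = 46.5 rounded down. At n = 50 (count 37.5) the interval would be 60.74-86.16%, which does not match.

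So the efficacy interval appears to allow for about 4 missing forms, while the acceptability interval and the 35/50 rule allow for none. Both items are on the same form.

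**Step 2: probability of meeting each rule.** Assumptions: true acceptability 80%, true efficacy 75%, answers independent, missingness unrelated to the answer. With m forms missing, n = 50 − m.
- Acceptability, missing counted against 50: P(X ≥ 35), X ~ Bin(n, 0.80).
- Acceptability, responders only: P(X ≥ r), with r the smallest integer at or above 0.7n.
- Efficacy, missing counted against 50: P(Y ≥ 26), Y ~ Bin(n, 0.75).

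| Missing m | n | Acceptability, out of 50 | Acceptability, responders (r) | Efficacy, out of 50 |
|---|---|---|---|---|
| 0 | 50 | 96.9% | 96.9% (35) | 99.99% |
| 3 | 47 | 86.9% | 96.3% (33) | 99.9% |
| 4 | 46 | 80.5% | 93.9% (33) | 99.8% |

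With 4 missing, the fixed rule asks for 35/46 = 76.1% acceptability among responders, not 70%. On a responder denominator, the efficacy rule is met with probability of at least 99.9% in every row.

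**Step 3: selection on a responder denominator.** This is an illustration with assumed rates: 80% acceptability in responders and 50% in those who miss LA1. With 4 of 50 missing (8%), the rate in all patients is 0.92 × 0.80 + 0.08 × 0.50 = 77.6%, against 80% reported. With 20% missing, well above the plan's estimate, it is 0.80 × 0.80 + 0.20 × 0.50 = 74%, against 80% reported. Both true values exceed 70%, so the bias affects the estimate more than the expected conclusion.

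**The case against.** The case for leaving the schedule alone has real content. The plan expects some loss at LA1, and the reminder, calls and staff help act inside the window. Those measures should keep missing forms low, although none of them reopens the window. The Interim column is not a general policy for missed forms: Decision Self-Efficacy is enrollment-only and has no Interim entry. A single timing is also defensible, because an answer at LA2 follows another BWS exposure and possibly early treatment. And the fall in pass probability comes from counting missing forms against 50, which is a gap in section 7.3.2 rather than in the schedule. That last argument stands, so the fix must settle the denominator too. Settling it alone, however, recovers no answers.

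A reader might infer two stronger claims that the documents do not support:
- *That patients who miss LA1 are lost to both endpoints.* The 1 year Questionnaire asks both items again, and the objectives in section 2.2 name no timepoint. It is a weak substitute, being late, restricted to those still participating, and assigned to neither rule, but the outcomes are measured again.
- *That the acceptability rule is likely to fail.* With 8 or 10 missing forms, P(X ≥ 35) would be 37.8% or 16.1%. But that is 16-20% missing, two to three times the plan's estimate, and no section supports such a rate. Nor can full rescue be assumed. If 6 of 10 missed forms were recovered, the probability would rise from 16% to 80.5% only if late responders share the 80% rate; at a 50% rate it would be about 58%.

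**Conclusion.** The point holds in a limited form. The only near-decision source for two stated conclusions is a form offered once, for 7 days, with no catch-up for patients who stay under follow-up. At the plan's own missing rate, the cost to the acceptability rule is a fall from 97% to about 80-87% if missing counts as failure. On responders it stays at about 94-96%, with a possible selection bias of unknown size. The efficacy rule is essentially untouched. These figures rest on 80% and 75% true rates and on missingness unrelated to the answer.

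Severity is low to moderate. The primary objective, content validity from the interviews, is not affected, and section 7.2 says the study is not powered for secondary endpoints. Section 7.3.2 nevertheless commits to a conclusion on each of the two, and the two rules treat missing answers to the same form differently.

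**What to change.** 1. In Table 5.1 and section 4.3.6, replace the first-timepoint restriction with: *LA1; if not completed at LA1, presented with LA2*.
2. In section 7.3.2, use the first completed Follow-up Questionnaire for both rules, flag forms completed at LA2, and repeat both results on LA1-window forms only.
3. In section 7.3.2, state one denominator for both rules and how a form still missing after LA2 counts. Bring the 35/50 rule and the two confidence intervals into line with it. Say also that the 1-year answers are reported separately, if that is the intention.

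The cost is one conditional two-item form in PRO Core, a table footnote and a few sentences in section 7.3.2, with no added visit. The downside is that late answers come about two weeks further from the decision and after another BWS exposure. The flag and the LA1-only results make that visible.
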